#### **7.1.4.1 Replacement policy**

##### **Phase Ib part:**

Participants will not be replaced on study. However, if a participant is considered as non-evaluable for the Dose Determining Set (DDS), enrollment of a new participant to the current cohort will be considered if there is less than the required number of evaluable participants. Enrollment of new participants may be considered until at least the minimum number (3) or at most the maximum number (6) of evaluable participants is achieved within the cohort. Minimum and maximum numbers of evaluable participants per cohort are defined in [Section 6.2.3](#).

##### **Phase II part:**

During the Phase II part no replacements will be needed.

#### **7.1.5 Withdrawal of informed consent/Opposition to use data/biological samples**

Participants may voluntarily withdraw consent to participate in the study/make opposition to use data/biological samples for any reason at any time.

Withdrawal of consent/opposition to use data/biological samples occurs when a participant:

- explicitly requests to stop use of their biological samples and/or data (opposition to use participant's data and biological samples)

and

- no longer wishes to receive study treatment

and

- does not want any further visits or assessments (including further study-related contacts).

This request should be in writing (depending on local regulations) and recorded in the source documentation.

Novartis will continue to retain and use all research results (data) that have already been collected for the study evaluation, including processing of biological samples that has already started at time of consent withdrawal/opposition. No new Personal Data (including biological samples) will be collected following consent withdrawal/opposition. If a participant withdraws consent, the investigator should make a reasonable effort (e.g. telephone, e-mail, letter) to understand the primary reason for this decision and record this information.

Where consent to the use of Personal and Coded data is not required in a certain country's legal framework, the participant therefore cannot withdraw consent. However, they still retain the right to object to the further collection or use of their Personal Data.

Study treatment must be discontinued and no further assessments conducted and the data that would have been collected at subsequent visits will be considered missing.

Further attempts to contact the participant are not allowed unless safety findings require communication or follow up.

If the participant agrees, a final evaluation at the time of the participant's consent withdrawal/opposition should be made as detailed in the assessment table (refer to [Section 7](#)).

### **7.1.6 Follow-up for safety evaluations**

#### **30-day follow-up**

All participants must have safety evaluations for 30 days after the last dose of investigational drug(s). At the end of this period, the investigator should assess and discuss with the participant any AE observed/concomitant medication taken since discontinuation of study treatment. This can be done via a phone contact.

Data collected should be added to the Adverse Events CRF and the Concomitant Medications CRF. Newly introduced antineoplastic therapies will be captured on the 'Antineoplastic therapies since discontinuation of study treatment' eCRF page.

Participants whose treatment is permanently discontinued due to an AE (clinical or based on abnormal laboratory value) must be followed until resolution or stabilization of the event, whichever comes first. In case of an abnormal laboratory value, blood tests should be repeated until resolution or stabilization.

#### **Post-treatment follow-up**

Any participant who discontinues from study treatment for any reason (except for death, disease progression, lost to follow-up, consent withdrawal/opposition or study termination) will continue to have tumor assessments performed every 8 weeks in the follow-up period until disease progression, death, lost to follow-up, end of study (Last Patient Last Visit, see [Section 4.3](#)), or withdrawal of consent/opposition to use data/biological samples.

Antineoplastic therapies since discontinuation of study drug will be collected during this follow-up period.

#### **Survival follow-up**

Upon completion of the 30-day follow-up or disease progression follow-up, all participants except those who withdrew consent for follow-up as a result of participant decision, or were lost to follow-up, will be followed for survival every 3 months (telephone call) until death or until the end of the study (Last Patient Last Visit, see [Section 4.3](#)). Participant's survival status may be collected via a phone call.

This visit does not apply for participants in Phase II Group 5.

### **7.1.7 Lost to follow-up**

For participants whose status is unclear because they fail to appear for study visits without stating an intention to discontinue from study treatment or discontinue from study or withdraw

consent /oppose to the use of their data/biological samples, the investigator should show "due diligence" by contacting the participant, family or family physician as agreed in the informed consent and by documenting in the source documents steps taken to contact the participant, e.g., dates of telephone calls, registered letters, etc. A participant should not be considered lost to follow-up until due diligence has been completed. Participants lost to follow-up should be recorded as such on the appropriate Disposition eCRF.

## 7.2 Assessment types

### 7.2.1 Efficacy assessments

Tumor response will be determined locally according to Response Evaluation Criteria in Solid Tumors (RECIST) 1.1 ([Appendix 1](#)).

Tumor response evaluations will be determined by the local investigators, based on RECIST 1.1. Imaging data will be centrally collected, checked for quality and stored for possible independent review by an imaging CRO designated by Novartis. Independent tumor response evaluations would then be determined according to the Novartis guideline ([Appendix 1](#)), based on RECIST 1.1. For Groups 1 to 4, the results of the central BIRC evaluations may be used for secondary analyses purposes.

CT/MRI scans will be performed at baseline within 28 days (preferably 7 days) before start of treatment and subsequently every 8 weeks from start of Cycle 3 until progression of disease and every 12 weeks from Cycle 13 Day 1 until progression of disease. See [Table 7-3](#) for details. CT/MRI scan will be performed at EOT if not conducted within 30 days prior to EOT. Disease progression follow-up should be performed as described in [Section 7.1.6](#). Depending on regulatory requirements it is allowed to have the EOT scan performed within an extended time frame but not later than 8 weeks from the last CT scan.

For participants in Phase II Group 5 entering the extension treatment period, a new baseline assessment should be performed no more than 28 days before the start of combination therapy. If the scan confirming disease progression on capmatinib monotherapy occurs within 28 days of the first dose of combination therapy, this scan may be used as the baseline scan for combination therapy.

After baseline, all assessments should be performed within  $\pm 7$  days of the scheduled day of assessment. Imaging evaluations subsequent to an off-schedule confirmatory scan should be performed according to the original assessment schedule. The same method of assessment and the same technique should be used to characterize each individual and reported lesion at baseline and during follow up.

If at baseline a participant has a medical contraindication to CT i.v. contrast or develops a contraindication during the trial, a non-contrast CT of chest plus contrast-enhanced MRI of abdomen is acceptable.

Participants with clinical evidence of bone metastases must have a whole body bone scan at baseline per local institutional practice (e.g., Tc99m bone scan, NaF positron emission tomography (PET) or whole body bone MRI). Lesions identified on the whole body bone scan at baseline, which are not visible on the chest and abdomen CT (or MRI) scan should be imaged

at baseline and followed at subsequent scheduled visits using localized CT, MRI or X-ray. After baseline, whole body bone scans need not be repeated, unless clinically indicated.

Skin lesions present at baseline should be documented using color photography, including a ruler, so that the size of the lesion(s) can be determined from the photograph. Skin photographs should be continued at subsequent tumor assessments for any lesions that were photographed at screening.

Baseline brain CT or MRI will be mandated for all participants prior to study treatment. Subsequent brain scans should only be conducted if brain lesions are documented at baseline for eligible participants or in participants that develop symptoms indicative of brain metastases.

All CRs and PRs must be confirmed by a second assessment not earlier than 4 weeks after the criteria for response are first met.

Any potentially measurable lesion that has been previously treated with radiotherapy should be considered as a non-measurable lesion. However, if a lesion previously treated with radiotherapy has clearly progressed since the radiotherapy, it can be considered as a measurable lesion.

PET/CT may be used only if the CT is of similar diagnostic quality as a CT performed without PET, including the utilization of oral and intravenous contrast media.

All participants discontinuing from the study for PD must have their disease progression documented by radiologic evaluation. In cases of clinically-evident disease progression, all efforts should be made to perform a radiologic evaluation.

Participants with symptoms of rapidly progressing disease without radiological evidence will be classified as progression only when clear evidence of clinical deterioration is documented and/or participant discontinued due to ‘Disease progression’ or death due to study indication.

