HCV testing	D	6.3.2. 7.2.2.5.5.		X	In cases of positive HCV-Ab, monitor HCV-RNA every 8 weeks, per Table 6-12 (or more frequently if clinically indicated).																	
Pregnancy test	D	7.2.2.5.6.		X	X						X					X			X			

	Category	Protocol Section	Screening Phase		Treatment Phase												Follow-Up				
			Molecular Pre-screening	Screening	Cycle 1						Cycle 2						Subsequent cycles	EoT	30-day Safety F/U	Disease progression E/I/LL	Survival F/U every 3 months
Day of Cycle				-28 to 1	1	2	8	15	16	22	1	2	8	15	22	1	15				
Imaging																					
Tumor evaluation as per RECIST 1.1 CT/MRI: - Mandatory at each evaluation: chest, abdomen - Mandatory if lesions at baseline: brain, skin - If clinically indicated: bone, other tumor sites	D	7.2.1.		X												X Every 8 wks (12 wks from C13D1)		X (if not conducted within 30 days of EOT)		X every 8 wks	
ECG (triplicate)	D	7.2.2.6.1.		X	X						X					X		X			
Safety																					
AEs	D	8.	X Procedural SAE only	X	Continuously																
Biomarkers																					
Molecular Pre-Screening (Tumor sample archival or newly obtained)		7.1.1. 7.2.4.	X																		
Whole Blood sample for determination of MET and EGFR status in cfDNA		7.2.4.		X*												X C3 and every third cycle		X			

	Category	Protocol Section	Screening Phase		Treatment Phase												Follow-Up						
			Molecular Pre-screening	Screening	Cycle 1						Cycle 2						Subsequent cycles	EoT	30-day Safety F/U	Disease progression E/IL	Survival F/U every 3 months		
Day of Cycle				-28 to 1	1	2	8	15	16	22	1	2	8	15	22	1	15						
Study Drug administration	D	6.1.1.			Continuously																		
PK sampling (Phase Ib part)	D	7.2.3.2.			X	X	X	X	X		X	X				X	C3 and 4 only						
PK sampling (Phase II part)	D	7.2.3.3.			X	X	X				X	X				X	C3 and 4 only						
Meal Recorded (Full PK participants)		6.1.1.			X						X												
Survival contact (telephone call)		7.1.6.																	X				
* Collect during screening phase or at C1D1 before the first dose of study drugs is administered.																							

Period	Category	Protocol Section	Screening		Treatment – Capmatinib Monotherapy			Extension Treatment (ET) – Capmatinib + Nazartinib combination therapy			Follow-up		
			Molecular pre-screening	Screening	Cycle 1	Cycle 2 and beyond	EOT	ET-Cycle 1	ET-Cycle 2 and beyond	ET-EOT	30-day Safety F/U	Post-treatment F/U	
Day of cycle			-	-28 to -1	1	1	-	1	1	-	-	-	

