**Table 7-3 Imaging collection plan**

Procedure	Screening/ Baseline	During Treatment/Follow-up	EoT/ Re-baseline
CT or MRI with contrast enhancement (Chest and Abdomen)	Mandated	Mandated, every 8 weeks ( $\pm 7$ days) Every 12 weeks ( $\pm 7$ days) from Cycle 13 Day 1.	>28 days from last assesment
Whole body bone scan	If clinically indicated	If clinically indicated	If bone metastasis is clinically suspected
Brain CT or MRI	Mandated	If brain positive at screening every 8 weeks ( $\pm 7$ days) Every 12 weeks ( $\pm 7$ days) from Cycle 13 Day 1. If brain negative at screening, as clinically indicated.	If brain positive at screening Or as clinically indicated if brain negative
Bone X-ray, CT or MRI (bone lesions only)	If lesions on bone scan that are not visible on the chest and abdomen CT/MRI	If bone lesions at screening every 8 weeks ( $\pm 7$ days) Every 12 weeks ( $\pm 7$ days) from Cycle 13 Day 1.	If lesions not visible on CT/MRI chest and abdomen

Procedure	Screening/ Baseline	During Treatment/Follow-up	EoT/ Re-baseline
Skin color photography (skin lesions only)	Mandated if skin lesions at screening	If skin lesions at screening every 8 weeks ( $\pm 7$ days) Every 12 weeks ( $\pm 7$ days) from Cycle 13 Day 1.	If skin lesions present
CT or MRI of other tumor sites (e.g., pelvis)	If clinically indicated	If lesions identified at screening every 8 weeks ( $\pm 7$ days) Every 12 weeks ( $\pm 7$ days) from Cycle 13 Day 1.	If clinically indicated

As per [Section 2.7](#), during a public health emergency as declared by local or regional authorities i.e., pandemic, epidemic or natural disaster, that limits or prevents on-site study visits, changes in collection of images (e.g., change of facility or frequency) can be listed as one of the risk mitigation procedures.

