#### **Best overall response**

BOR is the best response recorded from the start of the treatment until documented radiological disease progression/recurrence. However, any assessments taken more than 28 days after the last dose of study treatment will not be included in the best overall response derivation.

The study requires that for a partial response (PR) or complete response (CR) changes in tumor measurements must be confirmed by repeat assessments performed not less than 4 weeks after the criteria for the response are first met.

BOR will be summarized by treatment group.

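### In Groups 1 to 3 no scheduled scan can confirm a response first seen 0 to 20 days before a non-progression stop, and the scan cut-off for primary ORR is stated three ways

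*Protocol*

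**What the plan says.** The relevant rules stand in five places in the Protocol.

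- **Confirmation.** Section 7.2.1: "All CRs and PRs must be confirmed by a second assessment not earlier than 4 weeks". The same section mentions a confirmatory scan taken off schedule, but only to say that later imaging keeps to the original dates.
- **Scan schedule.** On treatment, Section 7.2.1 has scans "subsequently every 8 weeks from start of Cycle 3 until progression of disease", with a window of 7 days either side. After a stop for most reasons other than progression, Section 7.1.6 says participants "will continue to have tumor assessments performed every 8 weeks in the follow-up period".
- **End-of-treatment scan.** Section 7.2.1: "CT/MRI scan will be performed at EOT if not conducted within 30 days prior to EOT". Table 7-1 agrees: "X (if not conducted within 30 days of EOT". Table 7-3, to which Section 7.2.1 refers for detail, gives a different trigger: ">28 days from last assesment".
- **BOR cut-off.** Section 10.7.2.1, for Phase Ib and Groups 1 to 4: "any assessments taken more than 28 days after the last dose of study treatment will not be included in the best overall response derivation". The default in Appendix 1 (Section 14.1.3.1) is 30 days.
- **Primary variable.** Section 10.5.1 defines ORR in Groups 1 to 3 through a best overall response of confirmed CR or PR. It accepts confirmation whenever it occurs during the study and names no limit after last dose.

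**The concern.** The plan requires confirmation, but the scheduled visits do not supply a scan that its own BOR rule would count when treatment stops soon after the first response. If nobody orders an extra scan, an on-treatment responder who stops for toxicity is scored as a non-responder in the primary ORR and also leaves the DOR analysis, which is limited to confirmed responders. The error can only run downwards. ORR then partly reflects how early patients stop for toxicity as well as antitumour activity.

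The three cut-offs (none, 28 days, 30 days) can also produce different responder counts from the same data. For the primary endpoint of Groups 1 to 3 that choice should not be left open.

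**Working it through.** **Timeline.** Let x be the number of days from the first CR/PR scan to the last dose, and count days from the last dose. I assume that:

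- the first response scan was on its nominal date;
- the 8-week interval runs from that scan (Section 7.1.6 does not say; running it from EOT would be less favourable);
- the EOT visit falls within 7 days of last dose, as Section 14.1.4.2 says.

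The formulas are:

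- earliest valid confirmation: day 28 − x;
- next 8-weekly scan: day 56 − x, or 49 − x if taken 7 days early;
- last day that counts under Section 10.7.2.1: day 28.

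| x | Earliest valid confirmation | Next scan, nominal | Next scan, 7 days early | Counts? |
|---|---|---|---|---|
| 0 | 28 | 56 | 49 | no |
| 7 | 21 | 49 | 42 | no |
| 14 | 14 | 42 | 35 | no |
| 20 | 8 | 36 | 29 | no |
| 21 | 7 | 35 | 28 | only if early |
| 27 | 1 | 29 | 22 | only if early |
| 28 | 0 | 28 | 21 | yes |

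The next scan counts if 56 − x ≤ 28, that is x ≥ 28, or if 49 − x ≤ 28, that is x ≥ 21 when early. The EOT scan does not help for x up to 20: with EOT at most 7 days after last dose, the gap since the last scan is at most 20 + 7 = 27 days, below both the 28-day and the 30-day trigger.

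Two conditions narrow the gap. If the first scan was 7 days late and the next 7 days early, they are 56 − 14 = 42 days apart and the boundary falls to 42 − x ≤ 28, or x ≥ 14. If a long interruption puts EOT 21 days after last dose, then at x = 14 the last scan is 35 days old, so an EOT scan is due on day 21, which lies inside the valid window of days 14 to 28.

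**Unscheduled scan.** A scan from day 28 − x to day 28 satisfies both rules: day 28 alone at x = 0, days 21 to 28 at x = 7, days 14 to 28 at x = 14.

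**Response first seen y days after last dose.** The earliest confirmation is day 28 + y, so day 29 or later, and no scan can count under the 28-day limit. This can arise when both drugs are held before a stop: Section 7.1.4 requires discontinuation once either drug has been interrupted for 21 consecutive days or more.

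**The two EOT triggers.** At 29 or 30 days since the last scan, Section 7.2.1 and Table 7-1 waive a scan that Table 7-3 requires and that would be a valid confirmation. With EOT on the day of last dose, the next nominal scan falls on day 56 − 29 = 27 or 56 − 30 = 26 and still counts, so a response is lost only if that scan runs more than 1 or 2 days late.

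**Size, Group 3.** Success needs at least 22 responders of 40; the group may stop if fewer than 9 of 20 respond. With X1 and X2 each Binomial(20, p):

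- stop = P(X1 ≤ 8);
- success = Σ over a = 9 to 20 of P(X1 = a) × P(X2 ≥ 22 − a).

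At p = 0.55 this gives 0.1308 and 0.5533, matching 0.131 and 0.553 in Table 10-5; every other row also reproduces. If a share f of responders goes unconfirmed, p becomes p(1 − f). The Protocol gives no f, so 2% and 5% are assumptions.

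| True ORR | f | p(1 − f) | Futility stop | Success |
|---|---|---|---|---|
| 0.55 | 0 | 0.55 | 0.131 | 0.553 |
| 0.55 | 2% | 0.539 | 0.153 | 0.498 |
| 0.55 | 5% | 0.5225 | 0.191 | 0.415 |
| 0.65 | 0 | 0.65 | 0.020 | 0.923 |
| 0.65 | 2% | 0.637 | 0.026 | 0.895 |
| 0.65 | 5% | 0.6175 | 0.040 | 0.841 |

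The futility column assumes that confirmed responses are also used at the interim.

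**The case against.** A reader might infer that such a response cannot be confirmed at all and is always scored as a failure. The Protocol does not support that. Confirmation is mandatory, Section 7.2.1 foresees an off-schedule confirmatory scan, and the EOT waiver says when a scan is not needed without forbidding one. Section 7.1.4 also strongly recommends a tumour assessment before new therapy. For any response seen on or before the last dose, a compliant extra scan exists. This part of the objection stands. What remains is that no text or table tells a site to image a discontinued responder by day 28, that the slack is only x days, and that a response first seen after last dose has no route under the 28-day rule.

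Second, the 28-day rule sits among the secondary endpoints, so it may not apply to the primary ORR. That is possible, but Section 10.5.1 works through best overall response, and Section 10.7.2.1 is where the study defines that term. The text supports either reading, which is a reason to settle it.

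Third, a conservative cut-off is a legitimate choice, and the true ORR in Table 10-5 can be read as the rate of confirmed response, with unconfirmed cases already excluded. On that reading the table shows no loss of power. This also stands: the figures illustrate sensitivity and do not show an error in the design.

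**Conclusion.** The point holds as a gap in scheduling and definition. Under the stated timing assumptions, a CR or PR first seen 0 to 20 days before a non-progression stop in Groups 1 to 3 has no scheduled scan that could confirm it within the 28-day cut-off. At 21 to 27 days it depends on an early scan, and from 28 days the nominal scan suffices. If the response is first seen after last dose, no scan meets that cut-off. Separately, the primary ORR has three candidate cut-offs and the EOT scan two triggers.

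The number of participants affected cannot be derived from the Protocol. The fall in Group 3 success from 0.553 to 0.498–0.415 at a true ORR of 0.55 rests wholly on the assumed 2% to 5% loss, and on 0.55 being the rate that would be confirmed if a suitable scan were always taken. Every row of Table 10-5 reproduces, so it would be wrong to conclude that the printed operating characteristics are in error. Group 5 is outside the point: its estimand uses all response assessments after discontinuation, except those after a switch to the combination or new anti-cancer therapy.

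**What to change.** - **Sections 10.5.1 and 10.7.2.1:** state one rule for the primary ORR. A response first documented on treatment may be confirmed by the first follow-up scan that is at least 4 weeks later and precedes both progression and any new anti-cancer therapy. Say whether a response first seen during an interruption, after what proves to be the last dose, counts as on treatment, and that this rule replaces the Appendix 1 default.
- **Section 7.2.1, Tables 7-1 and 7-3:** use one EOT-scan trigger, more than 28 days since the last scan.
- **Sensitivity analysis:** repeat ORR with the 28-day cut-off.

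The first change is wording only and uses scans already planned. Its cost is that some responses are confirmed off treatment, which the sensitivity analysis makes visible. The second adds an EOT scan for participants at 29 or 30 days, whom Section 7.2.1 now exempts.

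Requiring an earlier scan instead would be weaker. It leaves one permissible day when the response is seen on the day of last dose, does nothing for a response first seen after it, and may add a scan, because Section 7.2.1 keeps later imaging on the original dates.
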